7.4 LOST TO FOLLOW-UP

A subject will be considered lost to follow-up if he or she repeatedly fails to engage for scheduled visits and is unable to be contacted by the study site.

The following actions must be taken if a subject fails to return to the clinic for a required study visit:

- The site must attempt to contact the subject and reschedule the missed visit as soon as possible and counsel the subject on the importance of maintaining the assigned visit schedule and ascertain whether or not the subject wishes to and/or should continue in the study.
- Before a subject is deemed lost to follow-up, the investigator or designee must make every effort to regain contact with the subject (where possible, 3 telephone calls and, if necessary, a letter to the subject's last known mailing address or local equivalent methods). These contact attempts should be documented in the subject's medical record.
- Should the subject continue to be unreachable, he/she will be considered to have withdrawn from the study.

8 STUDY ASSESSMENTS AND PROCEDURES

- Study procedures and their timing are summarized in the SoA (Section 1.3). Protocol waivers or exemptions are not allowed.
- Immediate safety concerns should be discussed with the Sponsor immediately upon occurrence or awareness.
- Adherence to the study design requirements, including those specified in the SoA, is essential and required for study conduct.
- All screening evaluations must be completed and reviewed to confirm that potential subjects meet all eligibility criteria. The investigator will maintain a screening log to record details of all subjects screened and to confirm eligibility or record reasons for screening failure, as applicable.
- Procedures conducted as part of the subject's routine clinical management (e.g., diagnostic status determination, ophthalmological examinations, blood count) and obtained before signing of the informed consent form may be utilized for screening or baseline purposes provided the procedures met the protocol-specified criteria and were performed within the timeframe defined in the SoA.
- Where study procedures coincide at the same time point, order of collection should be retinal imaging, ECGs, vital signs, blood draws where possible, provided that PK samples are collected within permitted windows. When ECG and vital signs occur at the same time, the rest time may be shared by the assessments.

8.1 OPHTHALMOLOGICAL AND RETINAL IMAGING ASSESSMENTS

8.1.1 Ophthalmological Exam

Eye exam (both eyes) will include:

- Slit lamp examination of the anterior segment of the eye
- Refraction (manual, autorefractor, lensometer, or historical)
- Visual acuity with Snellen eye chart
- Ophthalmoscopy examination, which may include OCT imaging as part of routine clinical care
- Intraocular pressure (contact or non-contact tonometry)
- Color fundus photograph

8.1.2 Triplicate Fundus Fluorescence (FF) Imaging

FF imaging enables visualization of fluorescent signals in the retina. Conventional and routinely used FF retinal cameras have the appropriate technical specifications to detect the hyper-fluorescent signal generated by AMDX-2011P-bound amyloidogenic proteins.

Predose images will be captured using fundus autofluorescence (FAF) imaging. Immediately after IV injection with study drug, FAF images and/or videos will be continuously captured until 2 minutes post-injection to assess the influx of the dye into the retina. After that, the remainder of the static images will be captured using FAF imaging. FF images (excluding conventional fundus photos) at all time points will be captured with the Heidelberg Spectralis 55-degree lens and the FAF settings of the device, using the central fixation target. Additional FF images may also be captured using the Optos UWF imaging modality or offset (no central fixation target) 55-degree Heidelberg FAF modality at select time points. Complete instructions information will be provided in the imaging section of the Study Reference Manual. Images will be quality checked and exported per the respective retinal imaging device User Manual. All FF images will be prepared and transferred to a central reading center for review. Each FF image will be reviewed by the masked reading center assessors using the respective retinal imaging device's native review software. The images will be assessed for image quality based on the respective devices image quality criteria.

On Day 1, retinal imaging will be performed with both Spectralis and Optos devices in triplicate as shown in Table 5. Due to intensity of imaging, images taken outside the windows will not be considered protocol deviation.

Table 5 Collection Timepoints for Fundus Fluorescence (FF) Imaging

Day 1 Time point	Window	Spectralis	Optos
Predose		X	X
0-1 min		Video	
2 min		X	
5 min		X	
10 min	±2	X	X
30 min	±5	X	X
1hr	±10	X	X
2hr	±10	X	X
4hr	±10	X	X
8hr	±10	X	X

8.1.3 Optical Coherence Tomography (OCT) and OCT Angiography (OCT-A) Imaging

OCT is a non-contact imaging technique which generates high resolution cross-sectional images of the retina and its corresponding layers. OCT images will be acquired as specified in the SoA (Section 1.3). The Heidelberg Spectralis device will be used to capture volumetric structural

OCT and OCT-A images. The combination of FF and OCT/OCT-A images will enable for detection and mapping of amyloidogenic protein distribution across the fundus and across different retinal layers and retinal plexuses. For each imaging modality, OCT and OCT-A, the images will be assessed for image quality based on the respective device's image quality criteria.

8.1.4 Central Retinal Image Center (CRIC)

All acquired images will be checked for quality, and subjects' identifiers will be removed by study personnel at investigational site. Deidentified images will be sent to a central imaging center specialized in assessing retinal images for detection and quantification of hyper-fluorescent puncta. Each assessor at the CRIC will be masked to the subject's disease status and sequence of post-injection images. Images will be batched and read at time of the interim analysis and final analysis, or more frequently at the request of SMC. Upon receiving deidentified images from the clinical site, quality assurance (QA) officer at the CRIC will review all images to confirm that the images sent meet the quality, quantity, and image acquisition criteria defined in the protocol. The QA officer will confirm that the images are labeled appropriately and that they were obtained by a certified imager. Once the QA officer reviews and confirms the integrity of each image batch, the images will be randomized and submitted to the masked assessors for grading. At the time of the interim and final analyses, the randomized masked images submitted to the assessors will be evaluated for image quality and for the number of distinct hyper-fluorescent puncta. Additional information will be provided in the imaging section of the Study Reference Manual.

8.2 SAFETY AND OTHER ASSESSMENTS

Safety assessments will include physical examination, ophthalmologic examination, vital signs, electrocardiogram (ECG), and laboratory assessments. Adverse events and concomitant medications will be monitored throughout the study.

8.2.1 Physical Examinations

- A complete physical examination will include, at a minimum, assessment of the Cardiovascular, Respiratory, Gastrointestinal, and Neurological systems.
- Height and body weight will be measured and recorded at screening.
- Investigators should pay special attention to clinical signs related to previous serious illnesses.

8.2.2 Vital Signs

- Systolic and diastolic blood pressure, heart rate, oral temperature, respiratory rate, and oximetry will be assessed.
- Blood pressure and heart rate measurements will be assessed using a completely automated device, with cuff wrapped around the non-dominant arm. Manual techniques will be used only if an automated device is not available.

- Subjects should be resting in a supine or semi-reclined position for at least 5 minutes prior to and during vital signs measurement obtained. When ECG and vital signs occur at the same time, the rest time may be shared by the assessments.
- Vital signs should be checked prior to blood draws when blood draws and vital signs occur at the same time.
- Additional vital signs may be performed at other times if deemed necessary.
- If deemed appropriate by the investigator, clinically significant findings in the vital signs will exclude a subject from study participation. Any abnormal finding related to vital signs that the investigator considers to be clinically significant must be recorded as an AE.

8.2.3 **Electrocardiograms**

- 12-lead ECGs will be obtained at the time points indicated in the SoA (Section 1.3) with the following parameters: HR, PQ (PR), QRS, QT, RR and QTcF along with information on T- and U-waves. Triplicate ECGs will be conducted on Day 1; single ECGs at all other time points.
- Subject to be resting in a supine position for at least 5 minutes prior to ECG. When ECG and vital signs occur at the same time, the rest time may be shared between the assessments.
- Investigator to record in eCRF if ECG is normal, abnormal (not clinically significant) or abnormal (clinically significant, with description of findings).
- In all cases in which an ECG has a potentially clinically significant finding, it will be repeated in triplicate within about 30 minutes and reviewed by the investigator or designee prior to subsequent dosing or study disposition decisions that do not constitute a subject emergency.
- Clinically significant findings in the ECG obtained at screening should exclude a subject from study participation (as deemed appropriate by the investigator). Any clinically significant change will be reported as an AE.
- Original paper tracings and tracing copies of the ECGs, including the interpretation, should be stored in the source documents. If ECG is thermal paper, it should be photocopied and then signed and dated since it fades over time.

8.2.4 **Clinical Safety Laboratory Assessments**

- See Section 10.2 for the list of clinical laboratory tests to be performed and the SoA (Section 1.3) for the timing and frequency.
- The investigator must review the laboratory report, document this review, and record any clinically relevant changes occurring during the study in the AE section of the eCRF. The laboratory reports must be filed with the source documents. Clinically

significant abnormal laboratory findings are those that are not associated with the underlying disease, unless judged by the investigator to be more severe than expected for the subject's condition.

- All laboratory tests with values considered clinically significantly abnormal during participation in the study should be repeated until the values return to normal or baseline or are no longer considered clinically significant by the investigator or Study Medical Monitor.
 - If such values do not return to normal/baseline within a period of time judged reasonable by the investigator, the etiology should be identified, and the Medical Monitor notified.
 - All protocol-required laboratory assessments, as defined in Section 10.2, must be conducted in accordance with the laboratory manual and the SoA (Section 1.3).
 - If laboratory values from non-protocol-specified laboratory assessments performed at the institution's local laboratory require a change in subject management or are considered clinically significant by the investigator (e.g., SAE or AE), then the results must be recorded in the eCRF.

8.3 PHARMACOKINETIC ASSESSMENT

Blood samples for determination of plasma concentrations of AMDX-2011P and AMDX-2011 will be collected as detailed in the SoA (Section 1.3). The timings of sample collection may be amended during the study conduct on the basis of emerging data to allow optimal characterization of the PK profile of AMDX-2011P and AMDX-2011.

Plasma concentrations of AMDX-2011P and AMDX-2011 will be measured by a specific and validated liquid chromatography-tandem mass spectroscopy (LC-MS/MS) method.

The following pharmacokinetic parameters (where appropriate) will be calculated by noncompartmental analysis from plasma concentrations of AMDX-2011P and for AMDX-2011 as defined in [Table 6](#).

Table 6 Pharmacokinetic Parameters

Parameter	Definition
C ₀	Back-extrapolated concentration at time = 0 hr (AMDX-2011P only)
C _{max}	Maximum observed drug concentration
T _{max}	Time of the maximum drug concentration
AUC _{0-last}	Area under the drug concentration-time curve from time zero to the last measurable concentration
AUC _(inf)	Area under the drug concentration-time curve from time zero to infinity
AUC _(0-t)	Area under the drug concentration-time curve from time zero to time t
t _{1/2}	Apparent terminal half-life
λ _Z	Apparent terminal elimination rate constant
CL	Systemic clearance (AMDX-2011P only)

Parameter	Definition
V _{ss}	Steady-state volume of distribution (AMDX-2011P only)

8.4 ADVERSE EVENTS AND SERIOUS ADVERSE EVENTS

8.4.1 Definition of Adverse Events (AE)

An AE means any untoward medical occurrence associated with the use of an intervention in humans, whether or not considered intervention-related (21 CFR 312.32 (a)).

8.4.2 Definition of Serious Adverse Events (SAE)

An AE or suspected adverse reaction is considered "serious" if, in the view of either the investigator or Sponsor, it results in any of the following outcomes: death, a life-threatening adverse event, inpatient hospitalization or prolongation of existing hospitalization, a persistent or significant incapacity or substantial disruption of the ability to conduct normal life functions, or a congenital anomaly/birth defect. Important medical events that may not result in death, be life-threatening, or require hospitalization may be considered serious when, based upon appropriate medical judgment, they may jeopardize the subject and may require medical or surgical intervention to prevent one of the outcomes listed in this definition. Examples of such medical events include allergic bronchospasm requiring intensive treatment in an emergency room or at home, blood dyscrasias or convulsions that do not result in inpatient hospitalization, or the development of drug dependency or drug abuse.

8.4.3 Classification of an Adverse Event

8.4.3.1 Severity of Event

AE severity will be evaluated by the investigator in accordance with the National Cancer Institute (NCI) CTCAE v5.0¹. For AEs that are not adequately addressed in the NCI CTCAE, the investigator should classify the intensity of the AE using the following guidelines:

- Grade 1: Mild: Aware of sign or symptom, but easily tolerated; no intervention needed
- Grade 2: Moderate: Discomfort enough to cause interference with usual activity, minimal non-invasive intervention indicated (e.g., short course of antibiotics)
- Grade 3: Severe: Medically significant but not immediately life-threatening; incapacitation with inability to work or do usual activity
- Grade 4: Life-threatening: Refers to an event in which the subject was at risk of death at the time of the event, as judged by the investigator; urgent/emergent intervention indicated. This category should not be used for an event that hypothetically might have caused death if it were more severe.
- Grade 5: Fatal outcome.

¹ Please refer to the CTCAE v5 at:

https://ctep.cancer.gov/protocolDevelopment/electronic_applications/docs/CTCAE_v5_Quick_Reference_5x7.pdf. Accessed March 30, 2022

It will be left to the investigator's clinical judgment to determine whether an AE is of sufficient severity to require the subject's removal from treatment or from the study. A subject may also voluntarily withdraw consent from treatment due to what she/he perceives as an intolerable AE. If either of these situations arises, the subject should be strongly encouraged to undergo an EOS assessment and be under medical supervision until symptoms cease or the condition becomes stable. An event is defined as 'serious' when it meets at least 1 of the predefined outcomes as described in the definition of an SAE, NOT when it is rated as severe.

8.4.3.2 Relationship to Study Drug

All AEs must have their relationship to study drug assessed by the clinician who examines and evaluates the subject based on temporal relationship and his/her clinical judgment. The degree of certainty about causality will be graded using the categories below. In a clinical study, the study product must always be suspect.

Relationship Scale	Definition
Definite	A reaction that follows a reasonable temporal sequence from administration of the study drug or in which the study drug level has been established in body fluids or tissue; that follows a known or expected response pattern to the suspected study drug; and that is confirmed by improvement on stopping or reducing the dosage of the study drug, and reappearance of the reaction on repeated exposure.
Probable	A reaction that follows a reasonable temporal sequence from administration of the study drug; that follows a known or expected response pattern to the suspected study drug; that is confirmed by stopping or reducing the dosage of the study drug; and that could not be reasonably explained by the known characteristics of the subject's clinical state.
Possible	A reaction that follows a reasonable temporal sequence from administration of the study drug; that follows a known or expected response pattern to the suspected study drug; but that could readily be produced by a number of other factors.
Unlikely	An event that does not follow a reasonable temporal sequence from administration of the study drug; that does not follow a known or suspected response pattern to the suspected study drug; and that could reasonably be explained by known characteristics of the subject's clinical state.
Not Related	Any event that does not meet the above criteria.

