2.3.1 Known Potential Risks

This is the first-in-human (FIH) study with AMDX-2011P. Though similar and higher doses of AMDX-2011P have been tested in multiple animal studies and results support the dose level to be tested in humans, this will be the first clinical exposure of the study drug; thus, there may be risks that are currently unknown.

There are no identified or potential risks of particular severity or seriousness anticipated on the basis of the mechanism of action of AMDX-2011P. The potential risks are based on theoretical considerations and findings ([Table 2](#)) from completed GLP nonclinical safety studies.

Table 2 Risk Assessment

Potential Risk of Clinical Significance	Summary of Data/Rationale for Risk	Mitigation Strategy
Potential Risks which may be associated with Study Drug		
Phototoxicity	Both AMDX-2011P and AMDX-2011 were suspected of being phototoxic in the in vitro	Subjects will be instructed to avoid direct sunlight and wear

Potential Risk of Clinical Significance	Summary of Data/Rationale for Risk	Mitigation Strategy
	3T3 neutral red uptake phototoxicity test; however, there was no evidence of ocular or cutaneous phototoxicity after IV administration of AMDX-2011P to pigmented rats at doses of up to 50 mg/kg followed by exposure to ultraviolet B, ultraviolet A, and visible light from a xenon lamp.	protective gear (e.g., sunglasses) for 24 hours after dosing. Ophthalmologic examinations will be conducted throughout the study.
Effect on eye	In male dogs, single IV bolus injections of 60 mg/kg AMDX-2011P resulted in mydriasis, minimal hyperemic conjunctiva and minimal to mild chemosis within 24 hours postdose, which was reversible within 6 days.	Ophthalmologic examinations will be conducted throughout the study.
Effect on cardiovascular function	In dogs, single IV bolus injections of 30 mg/kg AMDX-2011P resulted in transient reductions in systolic, diastolic, and mean arterial pressure and heart rate 15-30 min after injection. In vitro, inhibition of hERG channel was seen at high concentrations of AMDX-2011P.	Vital sign assessments, triplicate ECG recording

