7 STUDY DRUG DISCONTINUATION AND SUBJECT DISCONTINUATION/WITHDRAWAL

7.1 STOPPING RULES

The SMC will monitor safety throughout the study. The SMC will meet periodically to review available safety data to make decisions regarding continuation, modification, suspension, or termination of the study.

Study Stopping Rules

Dose escalation or administration of study drug in a dose cohort may be stopped and additional subjects will not receive study drug until a consultation has taken place among the investigator, the Study Medical Monitor (or designee), and SMC if one of the following circumstances occurs in subjects treated with AMDX-2011P unless it is determined by the SMC in consultation with investigator and the Study Medical Monitor that the occurrence is not related to the administration of the study drug:

- Two or more subjects in a cohort experience a Common Terminology Criteria for Adverse Events (CTCAE) Grade 3 or higher clinical or laboratory abnormality that is considered to be related to study drug by the investigator.
- An AE or group of AEs that singularly or in aggregate suggests to the investigator or Sponsor that the study drug is poorly tolerated and further treatment per protocol may not be safe.
- If one or more subject(s) in a cohort experience any treatment-related, treatment-emergent SAEs, dose escalation will be stopped to re-evaluate the dose in question.

If any of these criteria occur, the SMC will review all available data; if an event is determined to be related to a specific dose level, doses in subsequent cohorts may be modified or dose escalation may be terminated. Prior to any required dose level adjustment, the clinical and laboratory safety parameters from the previous dosing cohort(s) will be reviewed and discussed by the SMC to allow a recommendation on advancing to the next dose level. The suggested next doses may be the protocol-defined escalation dose, an equivalent dose, an intermediate dose, or an adjusted-downward dose based on evaluation of safety and tolerability data from previous cohorts.

The Sponsor, investigator, and the IRBs reserve the right to terminate or suspend the study at any time; the reason for such decision must be recorded. Should this occur, all data available will also be recorded in eCRFs. The investigator should notify the IRB in writing of the study's completion or early termination.

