7.2 DISCONTINUATION OF STUDY DRUG

Not applicable; this is a single dose study.

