6.7 Primary (Safety) Analysis

The primary analysis for this study will assess the safety of study drug, AMDX-2011P. Adverse Events will be coded by System Organ Class and Preferred Term using MedDRA, Version 25.0. The number and percentage of subjects experiencing treatment-emergent adverse events, serious adverse events, maximum severity to study drug, and highest relationship to study drug will be summarized by cohort and listed by subject ID for both eyes. Treatment emergent adverse events and serious adverse events leading to discontinuation will also be presented by count. Treatment emergent adverse events are defined as any AEs with an onset date on or after the date of the first dose of the investigational product or is pre-existing and worsens after administration. TEAEs severity will be measured by the severity scale: mild, moderate, severe, life-threatening, and fatal. The degree of certainty of causality will be graded using the following categories: definite, probable, possible, unlikely, and not related. A line listing of all treatment emergent adverse events will be provided including as reported verbatim term, SOC, PT, onset date, end date, severity, seriousness, causality, dose level, outcome and action taken with investigational product. Subjects with 1 or more than one TEAE per system organ class and preferred term will be counted once and be reported with the highest severity. In cases where severity or relationship are missing, the most conservative approach will be taken (i.e., highest severity and assumed to be related). Laboratory evaluations, vital sign assessments, and ECG parameters will be summarized using appropriate statistics at protocol-specified time points, as well as change-from-baseline at all protocol-specified post-baseline timepoints. Non-ocular adverse events will be summarized separately and listed by subject ID for both eyes.

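### Read literally, the causality definitions in Protocol 8.4.3.2 cannot grade some plausible drug reactions as related after a single first-in-human dose, which distorts the relationship summary and two stopping-rule inputs

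*Protocol*

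**What the plan says.** Protocol 8.4.3.2 defines five grades.

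- *Definite*: plausible timing (or drug measured in fluid or tissue), a known or expected pattern, and a reaction "that is confirmed by improvement on stopping or reducing the dosage of the study drug, and reappearance of the reaction on repeated exposure".
- *Probable*: plausible timing, a known or expected pattern, and a reaction "that is confirmed by stopping or reducing the dosage of the study drug; and that could not be reasonably explained" by the subject's clinical state.
- *Possible*: plausible timing and a reaction "that follows a known or expected response pattern to the suspected study drug; but that could readily be produced by a number of other factors"; neither dechallenge nor rechallenge is asked for.
- *Unlikely*: implausible timing, no known or suspected pattern, and another reasonable explanation.
- *Not Related*: "Any event that does not meet the above criteria".

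The lead-in to the same section rests the assessment on timing and clinical judgment and tells the assessor to regard the product as suspect throughout.

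On discontinuing study drug, Protocol 7.2 says "Not applicable; this is a single dose study". Protocol 2.3.1 calls the study first-in-human and warns that "this will be the first clinical exposure of the study drug; thus, there may be risks that are currently unknown".

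The grades feed two places. SAP 6.7 has causality "graded using the following categories: definite, probable, possible, unlikely, and not related" and summarizes the highest relationship by cohort, without saying which grades count as related. In Protocol 7.1, the first stopping trigger counts subjects with a Grade 3 or higher "clinical or laboratory abnormality that is considered to be related to study drug by the investigator", and the third counts treatment-related SAEs. The second, on poor tolerability, needs no causality grade.

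**The concern.** The definitions appear to have been written for repeated dosing of a drug with a known safety profile. With one injection there is no dose to stop or reduce and no re-exposure, so the top two grades describe evidence the study cannot produce. With no earlier human exposure, requiring a known or expected pattern screens out the new reactions a first-in-human study is there to find. Because the bottom grade is a residual, an event that fits nothing else is recorded as unrelated instead of unclassified.

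Two things are at stake. The relationship table could understate related events, or mix literal and judgment-based grading across sites. The relatedness input to two of the three stopping triggers could also be too low. Safety is the primary objective and the SMC escalates on safety data, so the wording matters more here than it would in a later trial.

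**Working it through.** The documents give no figure on this point, so there is nothing to reproduce. The check is logical, followed by one illustration on assumed rates.

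**Inputs.** From Protocol 8.4.3.2: T = plausible timing, K = known or expected pattern, D = dechallenge, R = rechallenge, A = alternative cause. From 7.2 and the single injection: D = R = 0.

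**Rules, applied in order.** *Definite* = T (or drug level), K, D and R. *Probable* = T, K, D and not A. *Possible* = T, K and A. *Unlikely* = not T, not K, and A. Anything else = *Not Related*. A measured plasma level can stand in for timing under *Definite*, but D and R are still required, so it does not help.

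**Profiles with plausible timing (T = 1).**

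| Pattern | Alternative cause | Literal (D = R = 0) | Recovery read as dechallenge (D = 1, R = 0) |
|---|---|---|---|
| Expected | Yes | Possible | Possible |
| Expected | No | Not Related | Probable |
| New | Yes | Not Related | Not Related |
| New | No | Not Related | Not Related |

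Literally, 3 of 4 fall to *Not Related*. On the looser reading, 2 of 4 do, and both are the new-pattern profiles.

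**Ordering.** Read literally, an expected-type event with no other explanation grades below the same event with many. On either reading, an event with implausible timing, no pattern and another explanation is *Unlikely*, one step above a new reaction minutes after injection with no other explanation.

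**Against other sections.** Protocol 8.4.3.3 calls an event unexpected if, among other things, its nature is inconsistent with the IB. Table 7 in 8.4.5 provides for SUSARs, which are both unexpected and suspected. An event unexpected in nature can hardly meet a known or expected pattern, so 8.4.3.2 tends to deny it the suspected status that SUSAR reporting presupposes. Protocol 8.4.6 asks of each SAE whether there is a reasonable possibility that the drug caused it, with no pattern or dechallenge condition. One SAE can therefore carry two conflicting causality answers.

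**SAP 6.7.** A missing relationship is assumed related, while a field completed by the literal definitions can read *Not Related*.

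**Illustration only.** Let p be the true per-subject rate of qualifying drug-caused events and q the share graded related. Both are assumed. The count graded related in a cohort of n is taken as binomial(n, pq). Cohort sizes of 3 to 9 and 12 are from Protocol 4.1, Table 3.

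First trigger (at least 2 subjects): 1 − (1 − pq)^n − n·pq·(1 − pq)^(n−1).

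- n = 12, p = 0.20: q = 1 gives 1 − 0.8^12 − 12(0.2)(0.8^11) = 0.725; q = 0.5 gives 1 − 0.9^12 − 12(0.1)(0.9^11) = 0.341.
- n = 12, p = 0.10: 0.341 falls to 0.118. n = 12, p = 0.30: 0.915 falls to 0.557.
- n = 9, p = 0.20: 0.564 falls to 0.225. n = 3, p = 0.20: 0.104 falls to 0.028.

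Third trigger (at least 1 subject), n = 12, p = 0.20: 1 − 0.8^12 = 0.931 falls to 1 − 0.9^12 = 0.718, if relatedness is taken from 8.4.3.2 alone.

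**The case against.** The best defence is that the grades express degrees of certainty under clinical judgment and are not a decision tree. A sensible investigator, told to keep the product suspect, would not call a prompt unexplained reaction unrelated. That is a fair account of the intent, but the residual definition says the opposite. Sites following the lead-in and sites following the definitions would grade the same event differently, so the text still needs reconciling.

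A reader might infer that drug reactions in general drop to *Not Related*. The documents do not support that. *Possible* needs neither dechallenge nor rechallenge, and Protocol Table 2 supplies expected patterns from nonclinical data: phototoxicity, eye effects, falls in blood pressure and heart rate, and injection site reactions. Such events reach *Possible* when another cause is also plausible, which may be common here; autonomic dysfunction, for example, is a core feature of MSA. The table's cells are also unweighted, so three of four is not a share of events.

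A reader might also infer that the stopping rules are disabled. They are not. The first trigger turns on the investigator's view and cites no grade in 8.4.3.2. The third concerns SAEs, which carry the separate 8.4.6 assessment. The second needs no grade, and the SMC reviews all available safety and tolerability data before escalation.

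**Conclusion.** The concern holds, within limits. It rests on a literal reading and on the single dose. On that reading *Definite* and *Probable* are unattainable, and three of four profiles with plausible timing are *Not Related*. Counting recovery as dechallenge reduces this to two of four, but new-pattern reactions remain ungradable as related.

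The effect is confined to the SAP 6.7 relationship summary and the relatedness input to the first and third triggers in Protocol 7.1. It would be wrong to conclude that events leave the primary safety result: SAP 5.1 counts all TEAEs and SAEs whatever their cause, and SAP 6.7 lists every TEAE. How many events would be misgraded cannot be determined from the documents. The trigger probabilities depend on assumed p and q and show direction only.

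**What to change.** Reword Protocol 8.4.3.2 for a single dose. Treat dechallenge, rechallenge and a known pattern as supportive evidence, not necessary conditions, and grade on temporal plausibility and the strength of any alternative cause. Define *Not Related* positively, as no plausible temporal relationship or clearly due to another cause, and not as the default. *Unlikely* currently also requires implausible timing, so the rewording must keep those two grades distinct.

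State in SAP 6.7 which grades are tabulated as related. The rule that a missing relationship is assumed related needs this too.

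The sponsor should reconcile the use of related across Protocol 7.1, 8.4.3.2 and 8.4.6, and check it against SUSAR reporting in 8.4.5. What should count as related for stopping is for the sponsor to settle; no criterion is proposed here and no threshold changes.

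The cost is protocol wording, matching eCRF completion guidance and one SAP sentence. Somewhat more AEs will be tabulated as related.
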